Aim 1: Evaluate comparative effectiveness of two patient decision aids (a long PDA versus a short PDA) and a surgeon-focused intervention (usual care versus intervention, a summary that includes patients' goals and treatment preferences) on their ability to achieve high decision quality.

Hypothesis 1.1: Overall, patients who receive the long PDA will have higher decision quality than those who receive the short PDA.

Hypothesis 1.2: Patients who receive the long PDA, with more comprehensive information and videos to make the information more salient, will have higher knowledge scores than those who receive the short PDA.

Hypothesis 1.3: More patients who receive the short PDA, with the explicit values clarification exercise, will have a clear treatment preference than those who receive the long PDA.

Aim 2: Follow participants for 12 months to determine the impact of the decision support strategies on treatment choices and health outcomes, specifically, overall quality of life and functional status.

Hypothesis 2.1: Patients with high decision quality (i.e. informed and received preferred treatments) at one week will have better health outcomes at one year compared to those with low decision quality.

Hypothesis 2.2: Patients with high decision quality at one week will have lower surgical rates at one year compared to those with low decision quality.

Aim 3: Identify patient-, physician- and intervention-level factors associated with effectiveness for the PDAs. These factors include (1) patient characteristics (e.g. age, gender, education level, and joint (hip or knee)), (2) provider characteristics (e.g. years since graduation, surgical volume), (3) intervention compliance (e.g. whether patients reviewed the decision aids and amount of time spent reviewing the decision aids) and (4) mode of delivery (online or hardcopy).

BACKGROUND AND SIGNIFICANCE

Provide a brief paragraph summarizing prior experience important for understanding the proposed study and procedures.

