This is a randomized trial with a 2x2 factorial design to examine the comparative effectiveness of two PDAs and an in-visit intervention. In the study, patients will be surveyed shortly before their initial visit with an orthopedic specialist and again about 1 week and 1 year after the visit. Patients scheduled for an appointment with the orthopedic specialist will be screened for eligibility (criteria are listed in Table 1) and if eligible, will be randomized to receive either the Health Dialog or Healthwise decision aids to review before their visit. A computer generated randomization allocation sequence will be created for participants. Eligible patients will receive a cover letter and an information sheet about the study that includes instructions about how to opt-out in the mail before their visit. Those who do not opt out will then be enrolled in the study. The random assignment originally assigned to patients who are found ineligible after their visit will be put back to the queue and become available for the next eligible patient.

Providers will be randomly assigned to usual care or intervention group (a worksheet which includes patient’s goals and preferences). Providers in the worksheet group will receive short training on the use of the worksheet.

The study will enroll patients at three sites: an academic center, the Arthroplasty Department at Massachusetts General Hospital (MGH), a community hospital, Kaplan Joint Center at Newton Wellesley Hospital (NWH), and an orthopedic specialty hospital, New England Baptist Hospital (NEBH). MGH and NWH share common resources that are critical to the conduct of the study, including patient registries which routinely collect similar patient reported data and clinical outcomes for hip and knee osteoarthritis patients. Both these sites also have access to both

[figure not shown]
Healthwise and Health Dialog decision aids through Partners Healthcare’s contracts with those vendors. NEBH is not a Partners-affiliated hospital and therefore requires separate coordination efforts to execute the research study.

Table 1: Eligibility for survey study

	Eligible	Ineligible

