Knee and Hip Osteoarthritis	
 • Diagnosis of knee or hip OA • Adults, age 21 or older • Scheduled new patient visit with participating orthopaedic specialist 	
 • Prior partial or total knee or hip replacement surgery on joint of concern within 5 years • Hip fracture or aseptic necrosis at any time in 12 months prior to visit • Rheumatoid arthritis or psoriatic arthritis • Does not read or write in English or Spanish • Unable to consent for self due to cognitive or other medical issue(s) • Prior decision aid order for joint of concern

Patient participants will be surveyed at three time points, before their visit with the surgeon, about one week after the visit, and again 12 months after the visit. Data from our previous studies suggests that we will have about 65 eligible new patients each month for the study enrollment period. We plan to enroll patients for about 12 months and estimate 1,120 patients will complete the first assessment in-clinic or before the visit with the surgeon, 840 (75%) will complete the second assessment one week after the visit, and 716 will complete the third assessment about one year after the visit. The sample size calculations consider both the potential for interaction effects between the interventions as well as the potential impact of clustering of patient participants within surgeons. Figure 2 offers a more detailed look at the projected screening and enrollment numbers.

Figure 2: CONSORT Flow diagram with estimates for screening, enrollment and response rates

Legend: PDA=patient decision aid, T1=in clinic before surgeon visit, PRO=patient reported outcomes; T2=1 week post visit; T3=6-12 month post visit

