14. About 6 months from the date of their initial visit, study staff will confirm participant surgical status and will send participants the third survey (T3) by mail or email. Non-surgical patients will receive T3 about 6 months from their consultation and surgical patients will receive T3 about 6 months from their surgery date. Study staff will follow up with a phone reminder within 1 week, a second mailing or up to three reminder emails as appropriate, and a second phone reminder for non-responders. For those who do not respond to the email reminders, we will mail them a survey before the second phone reminder.

15. All patients who receive the final survey will also be able to indicate their consent to be contacted in the future for other studies run out of the Health Decision Sciences Center. Of those patients who've given consent to be re-contacted: study staff may contact these patients via email or telephone, depending on their preferred method indicated, to invite them to participate in future projects and studies.

16. Study staff will review completed surveys soon after receipt and enter survey data into the study database as needed. If there are large portions of the surveys that are missing the study coordinator will contact the participant to determine whether the items were intentionally skipped

(in which case no further action will be taken) or whether it was not intentional and in this case will provide any needed clarification and request that the items be completed.

17. All participants who complete the T3 survey will receive a thank you note including an answer key to the knowledge section of the T1 and T2 surveys.

18. Study staff will collect additional data from the medical record (including patient demographics, treatments received for the hip/knee, co-morbidities, and clinician visits related to the hip/knee) in the 12 months since the initial visit, patient-reported quality of life and functional status data from the Harris Joint Registry and Newton Wellesley Hospital's Kaplan Joint Center registry (IRB# 2014P000696) databases, and use of decision aids from the Shared Decision Making database (IRB 2005p-002282).

19. Limited data will be kept on non-responders including joint, age, gender, physician, decision aid assignment, reason for refusal (if available), and all elements in the eligibility screener. This information will be used to examine non-response bias.

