- 9. PDA use (T1, T2):** items will assess how much of the DVD, booklet and/or website was reviewed (all, some, a little, none) and how much time did they spend reviewing it (0-5 minutes; 6-10 minutes; 11-20 minutes; 21-30 minutes; >30 minutes).
- 10. Treatment received (T3, chart review):** surgical and non surgical treatments tried in the twelve months after the visit will be self reported by patients and also collected via chart review.
- 11. Expectations (T2, T3):** 4 items will assess expectations for pain relief, limitations in daily activities, overall success of surgery and complications (29).
- 12. Demographics (T2):** information such as education, employment, marital status will be self reported.
- 13. Satisfaction (T2, T3):** questions to assess overall satisfaction with quality of visit or treatment outcome
- 14. Information use (T3):** 1 question to assess what sources of information patient about their health condition they found important
- 15. IMPACT index (T2, T3):** 7 items assessing the impact of hip and knee osteoarthritis on patients' perception of their condition: worry, pain, limitation, confidence, and involvement in decision making.

Table 3: Measures including in surveys

Measures	Pre-visit (T1)	~ 1 week (T2)	~ Follow-up (T3)
Visit goals and functional goals	2 (physician intervention group only)		
		12	

Decision Quality Instrument	9		0
Decision aid use	1	1	Not asked
Decision making process	0	11	7
Functional goals	Not asked	2	1
SURE	Not asked	4	Not asked
Expectations	Not asked	10	10
Quality of life, pain and functioning (KOOS or HHS, EQ-5D)*	Routinely collected	Not asked	Routinely collected
Decision Regret	Not asked	Not asked	5
Satisfaction	Not asked	1	2
Demographics and treatment history		5	2
Health literacy	1	Not asked	Not asked
Impact Index	Not asked	7	7
Total number of items	13 (MD usual care group)/ 15 (MD intervention group)	53	34
Total time estimate	5 minutes	15 minutes	15 minutes

*These items are asked as part of routine care at this time point.

Randomization and blinding

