11. A research coordinator will review medical record after the visit to complete the eligibility screener, as needed, and will send the second survey (T2) by mail or email within a week of the specialist visit to all confirmed eligible patients who did not opt out. If patients have not completed the routinely collected quality of life while at their visit, it will be included with this survey.

12. Study staff will follow-up with a phone reminder about one week after sending the survey, followed by a mailed reminder or up to three email reminders, and a second phone reminder for all the participants who did not complete the surveys. Participants who are receiving the survey by email will also get one mailed reminder if it is not completed in two weeks. Patients will be given the option to complete the survey by phone.

13. All participants who complete the T2 survey will receive a thank you note.

14. About 6 months from the date of their initial visit, study staff will confirm participant surgical status and will send participants the third survey (T3) by mail or email. Non-surgical patients will receive T3 about 6 months from their consultation and surgical patients will receive T3 about 6 months from their surgery date. Study staff will follow up with a phone reminder within 1 week, a second mailing or up to three reminder emails as appropriate, and a second phone reminder for non-responders. For those who do not respond to the email reminders, we will mail them a survey before the second phone reminder.

15. All patients who receive the final survey will also be able to indicate their consent to be contacted in the future for other studies run out of the Health Decision Sciences Center. Of those patients who've given consent to be re-contacted: study staff may contact these patients via email or telephone, depending on their preferred method indicated, to invite them to participate in future projects and studies.

16. Study staff will review completed surveys soon after receipt and enter survey data into the study database as needed. If there are large portions of the surveys that are missing the study coordinator will contact the participant to determine whether the items were intentionally skipped (in which case no further action will be taken) or whether it was not intentional and in this case will provide any needed clarification and request that the items be completed.

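### Hypothesis 2.1 promises a one-year health outcome, but step 14 sends the third survey about six months after consultation or surgery

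*Protocol*

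**What the plan says.** The protocol dates the third assessment in three ways.

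**One year or 12 months.** Hypothesis 2.1 defines high decision quality and sets its horizon in one line: "i.e. informed and received preferred treatments) at one week will have better health outcomes at one year". Aim 2 likewise speaks of 12 months of follow-up. Research Design and Methods has patients surveyed before the visit and "again about 1 week and 1 year after the visit", then repeats the schedule as "before their visit with the surgeon, about one week after the visit, and again 12 months after the visit". The enrolment projection expects that "716 will complete the third assessment about one year after the visit". The section on sharing data outside Partners describes the final data set as holding 12-month data.

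**About six months.** Step 14 appears in both Study Procedures and Recruitment Procedures. It opens "About 6 months from the date of their initial visit, study staff will confirm participant surgical status" and send out T3, and it continues "Non-surgical patients will receive T3 about 6 months from their consultation and surgical patients will receive T3 about 6 months from their surgery date".

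**A range.** The Figure 2 legend reads "T3=6-12 month post visit".

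The health measures behind Hypothesis 2.1 (EQ-5D, KOOS, HHS) are listed at T1 and T3 only. Step 18 adds a medical-record review covering 12 months from the visit. It also draws quality-of-life and function scores from the MGH and NWH registries.

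**The concern.** Because the health scores have no scheduled follow-up other than T3, the date of T3 is the date of the outcome unless another source supplies it. If step 14 is followed, a result written up as a one-year health outcome could rest on scores taken near month 6.

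There is a second consequence. Step 14 ties the survey date to treatment received, so time since the visit differs between surgical and non-surgical patients. The comparison in Hypothesis 2.1 is between patients with high and low decision quality, and high quality requires that the treatment received match the preference. Treatment therefore bears both on the grouping and on when the outcome is measured. At stake is what the trial can say under Aim 2 about later health.

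**Working it through.** **Reproducing the plan's own figures.** 840 / 1,120 = 75.0%, as stated. The 716 third assessments are 716 / 840 = 85.2% of the second-survey completers and 716 / 1,120 = 63.9% of those enrolled. The projection describes all 716 as one-year assessments. How many of them would be non-surgical is not given.

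**Timing under step 14.** Let s be the month of surgery after the visit and t the month at which T3 falls due. The documents give no value for s, so the values below are an assumed range. I read step 14 as a single status check at about month 6, since no later check is described.

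1. Not operated on by the check: t = 6. Shortfall against one year: 12 − 6 = 6 months.
2. Operated on by the check (s up to about 6): t = s + 6. Shortfall: 12 − (s + 6) = 6 − s months.
3. Operated on after the check, in months 7 to 12: these patients are non-surgical at the check, so t = 6, and T3 comes s − 6 = 1 to 6 months before surgery.

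| Patient | T3 due (months from visit) | Short of 12 by |
|---|---|---|
| No surgery by month 6 | 6 | 6 |
| Surgery at s = 1 | 7 | 5 |
| Surgery at s = 3 | 9 | 3 |
| Surgery at s = 6 | 12 | 0 |
| Surgery at s = 7 to 12 | 6 (before surgery) | 6 |

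T3 therefore reaches one year only for patients operated on at about month 6. The last row is a separate problem: the 12-month chart review would class these patients as surgical, while their T3 health score would describe them before the operation.

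**Does another source secure month 12?** In step 18 the 12-month window is attached to the medical-record items (demographics, treatments, co-morbidities, clinician visits). The registry scores follow in the same list with no time of their own. They may include one-year values, but nothing commits them to that.

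**A related mismatch.** Measure 10 uses T3 to collect self-reported treatments over the twelve months after the visit. A patient surveyed at month 6 cannot report on months 7 to 12.

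**Other hypotheses.** Hypotheses 1.1 to 1.3 do not use T3 health scores. Hypothesis 2.2 concerns surgery, and the 12-month chart review keeps its one-year horizon.

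**The case against.** The best defence is that step 14 is deliberate. Dating the survey from surgery gives operated patients a similar recovery time, and under rules 1 and 2 above t runs from 6 to 12, which is the range in the Figure 2 legend. That is a legitimate design, and nothing here rejects it. It does not rescue the wording: if it is the design, then Hypothesis 2.1, the design text, the projection and the data-sharing text describe something else.

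A second defence is that the health scores need not come from the T3 mailing. The Table 3 footnote says of them "These items are asked as part of routine care at this time point", and the registries might hold one-year values. This stands as a possibility, which is why the point is that a one-year outcome is not assured, rather than that none will exist.

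Third, Hypothesis 2.1 is not the primary hypothesis and compares groups by achieved decision quality, not by randomised arm. That is correct and limits the weight of the point.

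Some stronger readings are tempting but unsupported:

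- A reader might infer that every surgical patient is surveyed at s + 6. The month-6 status check confines that formula to patients already operated on by then.
- A reader might infer that NEBH has no follow-up health scores, because step 18 names only two registries and Table 3 marks the scores as routinely collected. Table 3 marks them the same way before the visit, yet NEBH patients complete them within the pre-visit study survey. The marking therefore does not exclude survey collection, and the measures list schedules them at T3 without a site exception.
- A reader might infer that the SAP never sets an outcome window. The sentence on Hypothesis 2.1 names a linear model with GEE and no window, but not all of the SAP text was available here, so no such claim is made.

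**Conclusion.** The point holds as an inconsistency in the current protocol text: a one-year horizon for Hypothesis 2.1 is stated but not secured. If the scores are taken at T3 under step 14, patients without surgery by month 6 are measured about 6 months early. Those operated on by then are measured 6 − s months early, and those operated on in months 7 to 12 are measured before their operation.

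This rests on two assumptions: that T3 supplies the scores, and that surgical status is settled once, at about month 6. A reader might go on to infer that the Hypothesis 2.1 comparison is biased in a particular direction. The documents do not support that. They give neither time to surgery nor the mix of treatments by decision-quality group, so neither direction nor size can be determined. The contradiction is certain; its effect on the estimate is not. It should be fixed, but it does not touch the primary outcome.

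**What to change.** Adopt one T3 rule and carry it through Hypothesis 2.1, the survey schedule and projection in Research Design and Methods, the Figure 2 legend, measure 10, step 14 in both places, and the data-sharing text. State the time window for the scores used in Hypothesis 2.1, including any taken from the registries. The documents do not settle which timing is intended; the investigators must.

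If step 14 stands:

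1. Restate Hypothesis 2.1 as the outcome at T3, about six months after consultation or surgery.
2. Report months from visit to outcome by decision-quality group and by treatment received.
3. Run a sensitivity analysis for patients whose T3 preceded their surgery.

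The cost is wording, one table and one analysis. The price is that the claim of a one-year health outcome is given up. If 12 months is kept instead, T3 mailing dates move and survey follow-up of non-surgical patients lengthens by about 12 − 6 = 6 months.

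### The knowledge answer key can reach non-surgical patients about 6 months before their H2.2 surgery outcome closes

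*Protocol*

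**What the plan says.** **Release of the key.** Protocol, Study Procedures, step 17 (repeated in Recruitment Procedures): "All participants who complete the T3 survey will receive a thank you note including an answer key to the knowledge section". The key covers the T1 and T2 knowledge items. No dispatch date is given. At T2, step 13 provides a thank-you note and mentions no key.

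**Timing of T3.** Step 14, also in both lists: "Non-surgical patients will receive T3 about 6 months from their consultation and surgical patients will receive T3 about 6 months from their surgery date". Research Design and Methods instead places the three surveys "before their visit with the surgeon, about one week after the visit, and again 12 months after the visit", and the Figure 2 legend has "T3=6-12 month post visit".

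**Treatment window.** Measures item 10 covers "surgical and non surgical treatments tried in the twelve months after the visit", by self-report and chart review. Step 18 sets the same 12-month period for the chart review.

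**Hypothesis at stake.** H2.2: "Patients with high decision quality at one week will have lower surgical rates at one year".

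**Primary endpoint.** The SAP counts a patient as a success for H1.1 if the knowledge threshold is met and the treatment received agrees with the stated preference. The available sentences give no time window for the treatment part.

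**The concern.** Holding the answers back until the last survey is sensible if that survey closes follow-up. For non-surgical patients under step 14 it does not. They are the patients whose surgery outcome is still open, and they can learn the correct answers with roughly half of the 12-month window to run. Patients already operated on get T3 about 6 months after surgery, so for them the key comes after the event.

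H2.2 compares one-year surgical rates between patients with high and low decision quality at one week, and being informed is part of that classification. The key has most to correct in patients who scored low. If it influences later choices at all, the likeliest direction is to move less-informed patients toward the informed ones in months 6 to 12 and shrink the contrast. It reaches T3 responders only, so exposure also depends on survey response.

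**Working it through.** **1. Order of events for a non-surgical patient, following the numbered steps**

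| Event | Time from visit | Source |
|---|---|---|
| Decision quality classified for H2.2 | about 1 week | Aim 2 hypotheses |
| T3 sent | about 6 months | step 14 |
| Key sent | after T3 is completed, no hold stated | step 17 |
| Treatment and surgery counted until | 12 months | step 18, Measures item 10, H2.2 |

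Window left when T3 is sent: 12 − 6 = about 6 months, less the time to return the survey and post the key. If T3 is at 12 months, the remainder is about 0.

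**2. How many could hold the key.** The protocol projects 1,120 patients at T1, 840 at T2 and 716 at T3.

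- Of all enrolled: 716/1,120 = 63.9%.
- Of T2 completers, which is closer to the H2.2 base because decision quality is taken at one week: 716/840 = 85.2%, if T3 completers are a subset of T2 completers.

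The 716 is described as completion at about one year and includes surgical patients. The number exposed inside the window cannot be computed, because no surgical rate or surgery timing is given.

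**3. Illustration for H2.2 (assumptions, not document figures).** Let *f* be the share of the surgery contrast that arises after month 6, assumed 15–30%. Let *r* be the share of those patients who hold the key. If the key removed the contrast completely in key-holders, the fraction lost would be *f* × *r*.

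| *r* | *f* = 15% | *f* = 30% |
|---|---|---|
| 63.9% | 0.15 × 0.639 = 9.6% | 0.30 × 0.639 = 19.2% |
| 85.2% | 0.15 × 0.852 = 12.8% | 0.30 × 0.852 = 25.6% |

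Complete removal is an extreme assumption. The table is still not a true upper bound, because both *f* and *r* are uncertain.

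**4. H1.1, only if it uses 12-month treatment.** The SAP states 89% power for 65% versus 83% with an effective 117 per group. Assume two-sided alpha 0.05, with pooled rate 0.74:

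- SE under the null: √(2 × 0.74 × 0.26/117) = 0.0574
- SE under the alternative: √((0.65 × 0.35 + 0.83 × 0.17)/117) = 0.0561
- Power: Φ((0.18 − 1.96 × 0.0574)/0.0561) = 88.6%, which agrees with the stated 89%.

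Now assume that 30–70% of analysed patients are non-surgical at 6 months and get the key, and that it alters later treatment in 1–10% of them. The altered share *a* runs from 0.30 × 0.01 = 0.3% to 0.70 × 0.10 = 7.0%. Take the pessimistic case in which every altered patient with high decision quality loses the match, equally in both arms. The rates become 0.65(1 − *a*) and 0.83(1 − *a*):

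- *a* = 0.3%: difference 17.9 points, power 88.2%
- *a* = 7.0%: difference 16.7 points, power 79.3%

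**The case against.** The case against has several parts.

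- **T3 timing is contradictory.** Research Design and Methods gives 1 year or 12 months, and at 12 months there is little left to influence. This stands as a limit. But step 14 is the detailed operating instruction, appears twice and fits the Figure 2 legend. Holding the key to month 12 is safe under either reading.
- **No dispatch date is given.** Early release is therefore an inference. True, but nothing in the text prevents it.
- **The mechanism is unproven.** H2.2 states an association with a composite at one week; it does not say that knowledge drives choice. The key answers five multiple-choice items for people already sent a decision aid and seen by a specialist. This stands, and is why the effect is probably small.
- **Delay has a price.** Patients who may still be deciding wait longer for correct answers. This stands as a cost.

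A reader might also infer that the key contaminates the primary endpoint. The documents do not support that. T1 and T2 knowledge scores are fixed before any key is sent. Measures item 1 lists the decision quality instrument at T3, but Table 3 appears to show no items for it there. Only the treatment-match part could move, and only with a 12-month window. Aim 2 speaks of decision quality at one week, and not all of the SAP was available for this check, so no omission is alleged.

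Nor do the documents support a bias between the decision aid arms. T3 completers in both arms get the key. H1.2 expects lower knowledge with the short aid, but a differential effect on later treatment is conjecture.

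**Conclusion.** The point holds for H2.2 as a minor weakness. Read together, steps 14, 17 and 18 allow the study to give corrective information to non-surgical T3 responders inside the one-year surgery window. The most plausible consequence is some dilution of the contrast between high and low decision quality; neither the direction nor the size is certain.

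The documents do not allow the size to be determined. The 10–26% loss of contrast in the H2.2 illustration rests on an assumed share of late surgery and on the key erasing the contrast entirely in those who hold it, so the real effect is probably much smaller. For H1.1 the issue is conditional on a 12-month treatment match. The conclusion depends on step 14 being the timing in force, and it largely falls away if T3 is at 12 months.

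**What to change.** 1. **Amend step 17** in both Study Procedures and Recruitment Procedures. Keep the thank-you note at T3, and send the answer key only once that patient's 12-month treatment window has closed.
2. **Reconcile the T3 timing** across Research Design and Methods, the Figure 2 legend and step 14. State the treatment window for H1.1 if the full SAP does not already do so.
3. **If keys have already been sent**, add one sensitivity analysis of H2.2, and of H1.1 if it uses 12-month treatment. Count surgery only up to a common cut-off of about 6 months after the visit for all patients. Do not cut each patient at their own key date: that would fix nearly all non-surgical responders as non-surgical while non-responders kept 12 months, so follow-up would depend on survey response and on the outcome itself. The common cut-off answers a 6-month question, so it supports the one-year analysis and does not replace it.

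**Cost.** A clause in two places and one extra mailing or email of at most about 716 keys. Non-surgical completers wait up to about 6 months longer for the answers.

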The heterogeneity of the treatment effect will be explored by testing the interaction between interventions and different factors on study outcomes. These factors include (1) patient characteristics (e.g., age, gender, education level, joint (hip or knee), health literacy and severity of disease), (2) provider characteristics (gender, years since graduation, surgical volume), (3) intervention compliance (whether patients reviewed the DAs) and (4) mode of DA delivery (online or paper). Linear or logistic regression models (with the GEE approach in the case of clustering within providers) will be used to test the interaction between interventions and these factors. We will also report treatment effect in each subpopulation if there are strong evidence of

interactions between interventions and these factors. Some of the hypothesis testing here might be exploratory in nature. The study will have sufficient power for testing interaction for continuous outcomes (e.g., detecting meaningful ‘differences in differences’ for knowledge scores, EQ-5D scores) but not categorical outcomes (e.g., rate of high decision quality, surgical rate).

References

2. Bland M. *Cluster randomized trials in the medical literature. Notes for talks presented at University of York*: University of York, 2005.

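### Self-reported education, a named effect modifier, is scheduled only at T2 with no other source named, so analyses of T1 outcomes by education may rest on a selected 75% of patients

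*Protocol*

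**What the plan says.** Protocol Aim 3 lists the patient-level modifiers as "patient characteristics (e.g. age, gender, education level, and joint (hip or knee", and the SAP's paragraph on heterogeneity of treatment effect lists "patient characteristics (e.g., age, gender, education level, joint (hip or knee), health literacy and severity of disease". Education is in both.

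The only time point given for education is in Protocol, Measures, item 12, labelled T2: "information such as education, employment, marital status will be self reported". In Table 3 the row "Demographics and treatment history" shows 5 items at T2 and 2 at T3. Its T1 cell is blank in the available copy, where several other rows state explicitly that a measure is not asked.

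On numbers, Research Design and Methods gives "estimate 1,120 patients will complete the first assessment in-clinic or before the visit with the surgeon" and "840 (75%) will complete the second assessment one week after the visit". The SAP sizes hypothesis 1.2 (knowledge) on about 560 patients per group, which is all 1,120 T1 completers. It says that the preference in hypothesis 1.3 is taken before the surgeon visit.

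Two other places bear on the source. Study Procedures step 18 collects demographics from the medical record without listing the fields. Step 19 describes what is held on people who do not respond: "Limited data will be kept on non-responders including joint, age, gender, physician, decision aid assignment", plus reason for refusal and the screener elements. Education is named in neither.

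**The concern.** Education is fixed before randomisation, but it is scheduled after the decision aid and the visit, and after the T1 outcomes it is meant to modify. For roughly 280 patients the T1 knowledge score and preference would exist while the modifier would not.

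A complete-case analysis of those outcomes by education then conditions on returning T2. If T2 response depends only on decision-aid arm and education, the interaction on knowledge is still estimated without bias. If it also depends on knowledge itself, or on something related to knowledge such as engagement with the aid, the estimate need not describe the enrolled population.

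Two further steps are affected. The SAP begins by comparing responders with non-responders, and education could not enter that comparison if it were seen only in responders. The imputation models would also lack education as an observed predictor in the patients whose T2 data are being imputed.

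**Working it through.** **Inputs.** T1 completers 1,120 and T2 completers 840 (Protocol, Research Design and Methods). Knowledge SD 20 and 560 per group (SAP, hypothesis 1.2). Minimal important change in knowledge 10 points (Protocol, Measures, item 1). Assumed here: two-sided alpha 0.05, and the share s of patients in one of two education strata, which the documents do not give. Clustering is ignored, as the SAP does for hypothesis 1.2.

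**1. The plan's own figures.** 1,120 × 0.75 = 840, as stated, leaving 1,120 − 840 = 280 (25%). For hypothesis 1.2 the detectable difference at 80% power is (1.960 + 0.842) × 20 × √(2/560) = 3.35 points against the stated 3.3. Power at 3.3 points is 78.8% against the stated 80%. Both agree closely, which supports reading hypothesis 1.2 as an analysis of all T1 completers.

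**2. Standard error.** With the same education mix, the interaction SE scales as √(1,120/840) = 1.155, an increase of 15.5%.

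**3. Detectable decision-aid-by-education interaction on knowledge.** SE = 20 × √(4/(N·s) + 4/(N·(1−s))), and the detectable difference is 2.802 × SE. For s = 0.5 and N = 1,120, SE = 20 × √(8/560) = 2.39, giving 6.7. For N = 840, SE = 20 × √(8/420) = 2.76, giving 7.7.

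| Assumed split | Detectable, N = 1,120 | Detectable, N = 840 | Power for 10 points, N = 1,120 | Power for 10 points, N = 840 |
|---|---|---|---|---|
| 50/50 | 6.7 | 7.7 | 99% | 95% |
| 30/70 | 7.3 | 8.4 | 97% | 91% |
| 20/80 | 8.4 | 9.7 | 92% | 83% |

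All detectable differences at N = 840 are below 10 points.

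**4. Table 3 item counts.** The T2 rows sum to 12 + 1 + 11 + 2 + 4 + 10 + 1 + 5 + 7 = 53 and the T3 rows to 0 + 7 + 1 + 10 + 5 + 2 + 2 + 7 = 34, both as stated. The T1 rows sum to 9 + 1 + 0 + 1 = 11, or 13 with the two goals items in the physician intervention group. The stated T1 totals are "13 (MD usual care group)/ 15 (MD intervention group". Two T1 items are therefore not allocated to any row in either group.

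**The case against.** The strongest reply is that education may already be available for T2 non-responders. Step 18 draws demographics from the chart and is not limited to T2 responders. The T1 total exceeds its listed rows by exactly two in both groups, next to a blank demographics cell, so one natural reading is that two demographic or treatment-history items are asked at T1 and the cell was left empty or lost when the PDF was read. Item 12's label is also not decisive, because the measures list and Table 3 disagree elsewhere: the decision quality instrument is listed for T3 but has 0 items there. This stands as a limit on the finding. Neither the chart fields nor the two items are identified as education, so the gap is possible but not proved.

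A reader might infer from step 19 that education is definitely missing for T2 non-responders. That does not follow. The list can be read as describing people who decline the study, whereas those who complete T1 and miss T2 are enrolled and fall under step 18.

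A reader might also infer that T2 non-responders cannot be imputed where education is involved. The SAP plans multiple imputation, and education could be imputed jointly from T1 health literacy, age, gender, site and T1 scores. What is lost is an observed predictor, and reliance on assumptions grows for something one question would settle.

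Finally, the SAP calls some of this testing exploratory, the models specified for hypotheses 1.1 to 1.3 do not name education, and a short T1 survey is a reasonable aim because completing it constitutes consent. These points keep the matter minor.

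**Conclusion.** The concern holds in a conditional form and is minor. T2 is the only stated time for self-reported education. If neither the chart nor the unallocated T1 items supply it, complete-case analyses of T1 knowledge and preference by education would use about 840 of 1,120 patients, selected by a response made after randomisation. Education would also be unobserved for T2 non-responders in the response comparison and the imputation models.

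Selection is the main issue, and the documents give nothing from which to size it. The precision cost is known and modest: 15.5% on the interaction SE, or 6.7 to 7.7 points with an even split and SD 20.

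It would be tempting to conclude that the SAP's claim of sufficient power for interactions on continuous outcomes fails. It does not: under every split tried, the detectable interaction on knowledge stays below 10 points even at 840. For preference, the SAP already disclaims interaction power on categorical outcomes. The conclusion rests on the projected 75% T2 completion, the assumed splits and alpha, and hypothesis 1.2 being analysed on T1 data, which is inferred from the 560 per group.

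**What to change.** Move the single education item from T2 to T1, beside the one-item health-literacy measure already there, and leave employment and marital status at T2. Change the timing in item 12 and fill the T1 cell of the Table 3 demographics row to match. In the same edit, allocate the two unassigned T1 items so that the T1 column adds up.

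If those two items already include education, no survey change is needed; correct item 12 and Table 3 only. If any patients have already passed T1 without the question, state which source supplies education for them.

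The cost is an edit to two surveys and one table. If the item is moved, T1 becomes one item longer and T2 one item shorter (53 to 52), so total patient burden is unchanged. The small downside is a slightly longer survey at the point where completion also serves as consent.
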